Anastomotic leaks are defined both clinically and radiographically. A clinical leak is defined by the appearance of enteric contents in an operatively-placed drain near the anastomosis or in a percutaneous drain placed post-operatively to evacuate a peri-anastomotic collection. A radiographic leak is one detected on cross-sectional imaging or by a contrast swallow study showing extravasation of oral contrast at the anastomosis. While patients undergoing bowel resection for benign disease are at risk of anastomotic leak, those undergoing surgery for cancer are at even greater risk as they often have poor nutrition and are subject to perioperative chemotherapy and radiation therapy. Anastomotic leaks result in prolonged hospitalization, immense health care costs, repeat procedures, and decreased quality of life, and in cancer patients, decreased survival(Yoo et al.). Patients who experience an anastomotic leak have 3x higher perioperative mortality than those who do not. Of those who survive the perioperative period, their long-term survival is also drastically reduced compared to patients who do not experience a leak(Mitchell).

Current techniques for esophageal anastomosis include hand-sewn and stapled closures with linear or circular stapling devices. Stapled closures are generally end-to-side if circular staplers are employed or side-to-side if linear staplers are used. Use of a linear stapler results in a remaining defect that must be sutures closed. All of these techniques are acceptable and choice depends on surgical approach and surgeon preference. No single technique has been definitively shown to be superior to the others.

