10.1 EVALUATION DURING TREATMENT/INTERVENTION

Clinical assessment for anastomotic leak will be carried out during the course of the hospitalization after surgery and up to 90 days +/- 14 days postoperatively. One radiographic assessment for leak will be performed during the interval from postoperative day 4-10. The grade of leak will be assigned according to standard criteria. For patients who die in the first 120 days following surgery where no documentation of leak has occurred, a request for autopsy will be made to determine the cause of death and will clarify whether or not a leak had occurred.

Clinical assessment for stricture will take place at 90 days +/- 14 days postoperatively. Patients will be evaluated in the outpatient clinic and will be assigned a dysphagia score from 0-4 by the RSA or clinical staff based on the following scale:

- 0 – Able to eat a normal diet
- 1 – Able to eat some solid food
- 2 – Able to eat semisolids only
- 3 – Able to swallow liquids only
- 4 – Unable to swallow anything

A dysphagia score of ≥ 2 will prompt further work up with upper endoscopy and possible dilatation if stricture is identified.

Patients may also be called by a member of the research team check on their health status until the study closes. This will allow for more robust data to be collected on the long term affects of the Gentrix implantation.

Data for cost metrics will be collected postoperatively through POD90 (+/- 14 days). These include metrics such as Length of Stay, Readmission, Complications, Reoperation and Total Hospital Bill. Total hospital bill data will be obtained from the Physician Billing Department. Data will be collected for all 86 patients enrolled and summarized. Cost of total hospital bill will be determined from the date of admission on protocol to day of discharge on protocol. Additional cost of re-admission to day of discharge of re-admission will so be included.

Examination/Intervention	Preop Visit(s)	OR	POD 4-10	POD21 (+/- 7 days)	POD90 (+/- 14 days)	Every 3 months until the study closes
Obtain Informed Consent	X					
Relevant / Interim Medical History	X			X	X	
Physical Exam	X					
Pre Surgical Testing	X					
Surgery		X				
Implantation of Gentrix PSM		X				
Thin-barium or Gastrografin Swallow Evaluation			X			

Dysphagia Score				X	
Symptom Assessment			X	X	
AE Assessment	X		X	X	
Review of the patient's medical record					X

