13.0 CRITERIA FOR REMOVAL FROM STUDY

The intervention in this trial is an isolated event (surgery), with routine post-operative care. Thus, there are no criteria to remove patients from the trial other than patient withdrawal of consent or death. Patients are permitted to withdraw consent at any time if they desire and will not undergo further trial investigations if they do so. Patients will be made aware that they cannot have the Gentrix PSM removed once it is implanted.

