14.0 BIOSTATISTICS

The historical control leak rate at our institution among patients receiving partial, total gastrectomy or esophagectomy is 8-15%: esophagectomy leak rate of around 15% and total and proximal gastrectomy leak rate of around 10%. A weighted average of 13% between the groups will be considered an unacceptable leak rate. We will employ Simon's two stage design to show a decrease in the leak rate assessed radiographically and clinically from 13% to 5% which would require 86 total patients to detect this difference with type I and II error rates of 10% each. In the first stage we will enroll 43 patients and if 5 patients experience a leak, then the study will be terminated, however if only 4 or less patients experience a leak then we will proceed to accruing up to 86 patients. If at the end of the second stage we see 7 or less leaks then we will consider the study worthy of further investigation. We expect two thirds of the accrued patients to have total gastrectomy performed while the rest to receive esophagectomy. Exact 95% confidence intervals will be computed for the leak rate for all the patients as well as separately for esophagectomy and total gastrectomy.

Similarly, the stricture rate will be estimated using binomial proportions and exact 95% CI will be computed.

The different cost metrics will be summarized descriptively: continuous cost metrics will be summarized using medians and ranges while binary variables will be summarized using binomial proportions.

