17.1 PROTECTION OF HUMAN SUBJECTS

Participation in this trial is voluntary. All patients will be required to sign a statement of informed consent, which will conform to MSKCC IRB guidelines.

1. Risks to the Subjects

Human Subjects Involvement and Characteristics: All patients at MSKCC who meet the inclusion criteria will be eligible. 86 patients will be entered on the trial; patients will be 18 years of age or older. Both men and women and members of all ethnic groups are eligible for this trial. This protocol does not include children because the number of otherwise eligible children is expected to be low. This statement is based on exclusion 4b of the NIH Policy and Guidelines on the Inclusion of Children as Participants in Research Involving Human Subjects.

2. Adequacy of protection against risks

Consent process:

All patients at MSKCC and participating sites who meet the inclusion criteria will be eligible. Participation in the trial is voluntary. All patients will be required to sign a statement of informed consent, which must conform to institutional IRB guidelines. Per MSKCC Policy, an IRB approved Consenting Professional listed on the face page of this trial will conduct the consent discussion with the patient and obtain written informed consent. The informed consent procedure is described in Section 18.

Possible Toxicities/Adverse Effects:

There are no known additional risks of Gentrix devices as described in Section 11.0.

Costs:

Gentrix PSM will be provided to Memorial Sloan-Kettering by ACell. Patients will not receive any compensation for participation in the study. In addition, subjects will not incur any additional costs as a result of participation in the study.

Alternatives:

The alternative to this trial is to have surgery without use of the Gentrix PSM, or have no surgery.

Confidentiality:

Every effort will be made to maintain patient confidentiality. Research and hospital records are confidential. Patients' names and any other identifying information will not be used in reports or publications resulting from this study. Other authorized agencies and appropriate personnel (e.g. qualified monitors from MSKCC) may review patient records as required.

Patient safety:

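### Do the leak limits of 4 in 43 and 7 in 86 need a written rule for patients whose leak status is never settled?

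*Combined protocol and SAP*

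**What the plan says.** Section 14.0 sets a Simon two-stage design with an unacceptable leak rate of 13%, a target of 5%, and both error rates at 10%. On the first stage it says: "In the first stage we will enroll 43 patients and if 5 patients experience a leak, then the study will be terminated". Four or fewer leaks lead on to 86 patients. The final rule is "If at the end of the second stage we see 7 or less leaks then we will consider the study worthy of further investigation". Exact 95% confidence intervals are planned for all patients and by operation. The section contains no definition of an evaluable patient, no replacement rule and no data cut-off for the stage 1 count.

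Other sections show that some patients may end with leak status unknown. Section 13.0 states that "there are no criteria to remove patients from the trial other than patient withdrawal of consent or death", and adds: "Patients are permitted to withdraw consent at any time if they desire and will not undergo further trial investigations if they do so". Section 10.1 plans one swallow study on postoperative day 4-10, with clinical leak assessment "carried out during the course of the hospitalization after surgery and up to 90 days +/- 14 days postoperatively". It also provides: "For patients who die in the first 120 days following surgery where no documentation of leak has occurred, a request for autopsy will be made". Section 17.1 gives the total: "86 patients will be entered on the trial". It neither allows nor forbids replacement.

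**The concern.** In a single-arm trial the leak count is the whole test. A patient with no recorded leak and no completed assessment adds nothing to that count. Scoring the patient leak-free and dropping the patient without replacement give the same decision, because fewer people are truly assessed against an unchanged limit. Both push toward success.

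The design sits almost exactly on its 10% limit, so one such patient is enough to exceed it. The opposite convention, counting the patient as a leak, costs much power. If the choice were made after the results were known, it could decide a close trial.

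The loss might also be related to leak. Section 3.2 says: "Patients who experience an anastomotic leak have 3x higher perioperative mortality than those who do not". That suggests deaths with unknown leak status could hide leaks.

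Two timing points add to the worry. Autopsy is requested for deaths up to day 120, while the clinical leak window closes at day 104 at the latest. And the stage 1 rule refers to enrolling 43 patients, not to 43 completed assessments.

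**Working it through.** **Inputs.** From section 14.0: n1 = 43, continue if 4 or fewer leaks; n = 86, success if 7 or fewer; rates 13% and 5%. From section 1.0: 86 patients in about 20 months, so 86/20 = 4.3 per month. From section 10.1: swallow at day 4-10; clinical window to day 76-104. The number of undetermined patients is not given; 1 to 6 of 86 is assumed.

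**The plan's own figures.** P(success | p) = sum over x = 0 to 4 of Bin(x; 43, p) × P(Bin(43, p) ≤ 7 − x).

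- At p = 0.13: 0.0989.
- At p = 0.05: 0.9012.

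Both meet the stated 10% error rates. A full search returns 43/4 and 86/7 as the Simon optimal design. The limits are therefore right for 43 and 86 assessed patients.

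**Undetermined patients contributing no leak.** With m1 and m2 such patients in stages 1 and 2, replace 43 by 43 − m1 and 43 − m2 and keep the limits. The last column counts the same patients as leaks instead. As designed, power at 5% is 90.1%.

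| m1, m2 | False success at 13%, no leak contributed | Power at 5% if counted as leaks |
|---|---|---|
| 0, 1 | 10.5% | 84.9% |
| 1, 0 | 10.6% | 78.8% |
| 1, 1 | 11.3% | 71.5% |
| 2, 2 | 12.8% | 38.6% |
| 3, 3 | 14.6% | 8.6% |

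The middle column is an upper bound when undetermined status is unrelated to leak. It gives these patients no chance of a recorded leak, whereas someone who misses only the swallow can still have a clinical leak detected.

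**Are deaths without a documented leak enriched for leaks?** Take the threefold mortality from section 3.2 and a 13% leak rate. Among deaths, leak to no-leak odds are 3 × 0.13 to 0.87, that is 0.39 to 0.87. A patient who dies after a documented leak is already counted. If a fraction u of the leaks among deaths goes undocumented, the leak share of deaths with no documented leak is 0.39u / (0.39u + 0.87).

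- This equals 13% when u = 0.13/0.39 = 1/3, so enrichment needs more than a third of these leaks to be missed.
- At u = 0.2 the share is 0.078/0.948 = 8.2%, which is below 13%.
- With 2, 4 or 6 such deaths at u = 0.2, the leak rate in the remaining patients is (0.13 × 86 − 0.082m)/(86 − m). False success is then 10.7%, 11.7% or 12.6%, lower than in the table.

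The documents give no value for u. Most deaths after day 10 should also have had a swallow, which narrows the group further.

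**Stage 1 timing.** When the 43rd patient is operated on, those still inside the clinical window number 4.3 × 76/30.44 = 10.7 to 4.3 × 104/30.44 = 14.7. Those still within day 10 number only 4.3 × 10/30.44 = 1.4; the rest should have had their swallow. If pending leaks are missed at stage 1 but counted at the end, the extreme case is a trial that never stops early: P(Bin(86, 0.13) ≤ 7) = 0.115. With 13 or 15 patients pending and none of their leaks yet known, final false success is 11.2%.

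**Scale against the benchmark.** Section 14.0 expects two thirds gastrectomy (leak rate around 10%) and one third esophagectomy (around 15%). That mix gives (2 × 10 + 15)/3 = 11.7%. At 11.7% the unchanged rule passes 17.5% of the time. Uncertainty in the rounded benchmark therefore moves the pass rate more than one or two undetermined patients do.

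**The case for a change.** The strongest case for a change is that the direction of the gap is known, the margin is only 0.1 percentage points, and a few sentences would close it. The autopsy request helps to find leaks but is not a counting rule, and nothing covers an autopsy that is not done. Patients consent before surgery and can be excluded intraoperatively, and the plan does not say whether they count toward 43 or 86.

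The silence is real and the bias, where there is any, favours the device. That much stands. The size does not support more. The harm depends on an assumed number of patients and is about 0.6 to 0.8 points for one. The argument from mortality holds only if more than a third of leaks in dying patients go undocumented, which nothing in the documents indicates.

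The plan also has partial safeguards: leak can be found by swallow or clinical course, autopsy is requested to day 120, and nothing says that a leak recorded before withdrawal is discarded.

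The stronger remedies are not free. Scoring one undetermined death as a leak costs 90.1 − 84.9 = 5.2 to 90.1 − 78.8 = 11.3 points of power. Replacing withdrawals adds enrolment and preserves the error rates only if withdrawal is unrelated to leak. Waiting for complete stage 1 windows takes up to 104/30.44 = 3.4 months.

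**Conclusion.** No change to the plan follows. Section 14.0 leaves a rule unwritten, but its limits are correct and its error rates reproduce at 9.9% and 90.1% power. Analysts would sensibly fill the gap: count a leak found by either route, take as evaluable those who received the device and have a recorded leak or completed assessment, and show the result with undetermined patients scored both ways. The same reporting can state how a leak found at autopsy between days 104 and 120 was handled.

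With 1, 2 or 4 undetermined patients, false success is at most 10.5-10.6%, 11.3% or 12.8%. Incomplete stage 1 data alone cannot take it above 11.5%. These figures assume that undetermined patients have the same leak rate as the rest and, for stage 1, that pending leaks are counted later. The conclusion would weaken if many patients were undetermined (six give 14.6%) or if leaks in dying patients were commonly missed. The documents point to neither. Going further, by scoring deaths as leaks, replacing withdrawals or pausing at stage 1, is a trade-off for the sponsor and not the correction of an error.

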We plan to accrue 86 patients 76 of which will be accrued at MSK. We expect that accrual will last about 20 months. With follow up of 90 days (+/- 14 days) to evaluate for stricture, we expect the total study time will be 24 months.

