16.2 Quality Assurance

Monthly registration reports will be generated to monitor patient accruals and completeness of registration data. Routine data quality reports will be generated to assess missing data and inconsistencies. Accrual rates and extent and accuracy of evaluations and follow-up will be monitored periodically throughout the study period and potential problems will be brought to the attention of the study team for discussion and action. Random-sample data quality and protocol compliance audits will be conducted by the study team, at a minimum of two times per year, more frequently if indicated.

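### Does section 14 need a rule that closes accrual at the 8th leak, and a statement that a late-found 5th stage 1 leak counts?

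*Combined protocol and SAP*

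**What the plan says.** Section 14.0 (Biostatistics) sets a Simon two-stage design for a fall in leak rate from 13% to 5%, with type I and type II error of 10% each. The stage 1 rule is: "In the first stage we will enroll 43 patients and if 5 patients experience a leak, then the study will be terminated". With 4 or fewer leaks the trial goes on, with 86 as the ceiling. The final rule is: "If at the end of the second stage we see 7 or less leaks then we will consider the study worthy of further investigation". On estimation, the section states: "Exact 95% confidence intervals will be computed for the leak rate for all the patients as well as separately for esophagectomy and total gastrectomy".

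Section 10.1 defines when a leak can be found. Clinical assessment covers "hospitalization after surgery and up to 90 days +/- 14 days postoperatively", with one contrast swallow on day 4-10. For patients who die "in the first 120 days following surgery where no documentation of leak has occurred, a request for autopsy will be made". The same section says of the cost metrics: "Data will be collected for all 86 patients enrolled and summarized".

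Section 16.2 provides general oversight: "Accrual rates and extent and accuracy of evaluations and follow-up will be monitored periodically throughout the study period". It sets no stop based on the leak count. Section 1.0 gives the pace: "We expect that accrual will last about 20 months".

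**The concern.** Two gaps suggest themselves.

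1. **Enrolment after the answer is known.** Success needs at most 7 leaks, so the 8th leak makes the trial negative whatever follows. Section 14.0 applies the limit only at the end of stage 2. Further patients could receive an implant that, under section 13.0, cannot be removed, in a trial whose primary result is already fixed.

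2. **A late 5th leak in stage 1.** Leaks can surface up to about day 104, or through an autopsy after a death up to day 120. Section 14.0 does not say when the stage 1 count is read or whether accrual pauses. A 5th leak among the first 43 could come to light after stage 2 has opened. If the decision to continue were then left to stand, more ineffective-device trials would reach the final test, and type I error could exceed the stated 10%.

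**Working it through.** **Inputs.** Section 14.0: p0 = 0.13, p1 = 0.05, n1 = 43 (continue with at most 4 leaks), N = 86 (success with at most 7). Section 1.0: 86 patients in about 20 months, so 86/20 = 4.3 per month. Section 10.1: leak window to day 90 + 14 = 104.

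**Step 1: reproduce the plan's error rates.**

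P(success | p) = Σ over x = 0..4 of P(X1 = x) × P(X2 ≤ 7 − x), with X1 and X2 independent Binomial(43, p).

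| x | P(X1 = x), 13% | P(X2 ≤ 7 − x), 13% | product | P(X1 = x), 5% | P(X2 ≤ 7 − x), 5% | product |
|---|---|---|---|---|---|---|
| 0 | 0.0025 | 0.8112 | 0.0020 | 0.1102 | 0.9988 | 0.1101 |
| 1 | 0.0161 | 0.6768 | 0.0109 | 0.2494 | 0.9949 | 0.2481 |
| 2 | 0.0506 | 0.5066 | 0.0256 | 0.2756 | 0.9806 | 0.2703 |
| 3 | 0.1033 | 0.3268 | 0.0337 | 0.1982 | 0.9377 | 0.1859 |
| 4 | 0.1543 | 0.1725 | 0.0266 | 0.1043 | 0.8334 | 0.0870 |

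Without rounding the terms, the sums are 0.0989 (type I error) and 0.9012 (power). Both meet the 10% limits. A search over two-stage designs with N from 60 to 100 that meet these limits finds 43/4 and 86/7 to have the lowest expected sample size at 13%: 43 + 43 × 0.32676 = 57.05.

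**Step 2: effect of closing at the 8th leak.** Every path with 8 or more leaks already fails, so closing there removes no success. Type I error and power stay at 0.0989 and 0.9012.

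At 13%, P(fail in stage 2) = P(pass stage 1) − P(success) = 0.32676 − 0.09891 = 0.22785. In those trials the 8th leak falls at median patient 71 (quartiles 64-78), with a mean of 15.15 patients after it. The mean saving over all trials is 0.22785 × 15.15 = 3.45.

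| True leak rate | P(fail in stage 2) | Expected N, plan | Expected N, closing at 8th leak | Saving |
|---|---|---|---|---|
| 13% | 0.228 | 57.05 | 53.60 | 3.45 |
| 10% | 0.246 | 67.40 | 64.32 | 3.1 |
| 5% | 0.036 | 83.32 | 82.99 | 0.3 |

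These savings assume instant recognition. At 4.3 patients per month, delays of 10, 90 and 104 days let in 1.4, 12.7 and 14.7 further patients. The saving at 13% then falls to 3.14, 1.15 and 0.91.

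**Step 3: what would be given up.** With the 8th leak at patient 71, the ordinary exact 95% interval for 8/71 is 5.0-21.0%; a full trial ending at 10/86 gives 5.7-20.3%. The esophagectomy third would shrink from about 29 to about 24 patients, for example 4/24 (4.7-37.4%) against 4/29 (3.9-31.7%). The stricture and cost summaries would lose the same patients.

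**Step 4: would the planned intervals need changing?** Enumerating all outcomes for true rates from 2% to 30% in steps of 0.1 points, the ordinary Clopper-Pearson interval for the overall leak rate has minimum coverage 95.2% under the plan and 95.3% with closure at the 8th leak. The mean of leaks/N at 13% is 13.9% either way; at 5% it is 5.2% without closure and 5.3% with it. No special estimator is called for.

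**Step 5: the late 5th leak.** Section 14.0 ties termination to 5 of the first 43 patients having a leak and attaches no date. Section 10.1 makes a leak found up to day 90 +/- 14 a leak for this trial. Applied as written, a late leak counts and type I error is 0.0989.

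Inflation arises only if the decision to continue is upheld against that text. The documents give no leak timing, so its size depends on assumptions:

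- A share of 10-50% of leaks surfacing evenly over days 10-104, even accrual, and the stage 1 count read at patient 43's day 10: 0.0999-0.1036.
- A share of 10%, 20% or 30% of stage 1 leaks all missed at the stage 1 decision and counted only in the final total: 0.104, 0.108 or 0.111.
- Stage 1 never applied: P(Binomial(86, 0.13) ≤ 7) = 0.1149, the ceiling.

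**The case for a change.** The best case for a change is that it costs a few sentences and no error rate. Closing at the 8th leak would spare on average 15 patients in the 22.8% of trials at 13% that fail in stage 2, and almost nothing is lost if the device works. Most radiographic leaks should be known by the day 4-10 swallow, so the realistic saving may lie nearer 3.1 than 0.9. Settling the late-leak case beforehand would also avoid a ruling made with results in view, and under a lenient reading type I error can pass 10%.

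Much of this is true as arithmetic, and a team could reasonably adopt either sentence. It does not show a fault. Eight leaks in 86 is 8/86 = 9.3%, below the 13% null, so the 8th leak is no sign of harm that would oblige a stop. The number 86 is a ceiling, so nothing forces the team to fill stage 2. Full accrual also serves stated aims: procedure-specific intervals, the stricture rate and a cost summary planned for all 86. The late-leak inflation needs both an assumed timing and a decision contrary to the written rule. An explicit sentence would confirm the rule and not alter it.

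**Conclusion.** The concern does not hold. The plan's design meets its stated error rates (0.0989 and 0.9012), and having no stop inside stage 2 is standard for Simon's method. Closing at the 8th leak would leave the error rates and the trial's conclusion unchanged. It would trade an average of about 0.9 to 3.45 patients at a true 13%, depending on recognition delay, and about 0.3 or fewer at 5%, against somewhat less secondary and subgroup information. That is a design preference.

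The late 5th leak is covered by reading sections 14.0 and 10.1 together: the rule has no time limit, so the leak counts and type I error stays at 0.0989. This rests on the natural reading that the first-stage rule means 5 or more leaks among the first 43 patients, whenever found in the leak window. The saving figures further assume a constant leak probability across patients and even accrual at 4.3 per month.

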3.3 Preliminary Data

We have performed a pilot study of 28 patients undergoing total gastrectomy via open or minimally-invasive approach to determine the feasibility of extraluminal reinforcement of the esophagojejun al anastomosis with Gentrax. In this series of patients we determined that this technique is feasible in both open and minimally-invasive procedures and that it adds essentially no time to the procedure and introduces no toxicity or side effects. Of the 28 patients, 1 experienced a clinical anastomotic leak for a rate of 3.6%.

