6.2 Subject Inclusion Criteria

- Patient 18 years of age or older
- Pathologically confirmed Gastric, Gastroesophageal Junction (GEJ) or Esophageal, adenocarcinoma at either MSKCC or a participating site (biopsy may be performed at other institutions but slides must be confirmed at MSKCC or a participating site, as is routine care at our institution)
- Patient undergoing any resection requiring an anastomosis to the esophagus for curative intent. Including but not limited to esophagectomy or total gastrectomy.
- Subject is willing to provide written informed consent

- Subject is willing and able to comply with the follow-up regimen

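### One fixed pooled leak cut-off is used although the historical leak rates differ by procedure and the procedure mix is only expected, so the 10% type I error holds only near one particular mix

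*Combined protocol and SAP*

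**What the plan says.** All of the decision rule is in Section 14.0 (Biostatistics).

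- Historical rates by procedure, in per cent: "esophagectomy leak rate of around 15% and total and proximal gastrectomy leak rate of around 10".
- Benchmark: "A weighted average of 13% between the groups will be considered an unacceptable leak rate".
- Target and size: a fall "from 13% to 5% which would require 86 total patients", with "type I and II error rates of 10% each".
- Stage 1: "In the first stage we will enroll 43 patients and if 5 patients experience a leak, then the study will be terminated". With 4 or fewer leaks, accrual continues to 86.
- Final rule: 7 or fewer leaks among the 86 means that the approach merits further study.
- Mix: "We expect two thirds of the accrued patients to have total gastrectomy performed while the rest to receive esophagectomy".

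Section 7.0 (Recruitment Plan) gives matching approximate numbers by clinic: 57 patients from the GMT clinics and 29 from the Thoracic clinics. Section 6.2 sets no limit by procedure; it admits a "Patient undergoing any resection requiring an anastomosis to the esophagus for curative intent". The registration procedure in Section 15.2 checks eligibility and consent only. Procedure enters the analysis only through separate exact 95% confidence intervals, which play no part in either decision.

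**The concern.** The trial has no concurrent control, so everything rests on comparing a leak count with a historical rate. That historical rate depends on which operations are done. If more gastrectomies are enrolled, fewer leaks are expected even when the device does nothing, yet the threshold stays at 7. If more esophagectomies are enrolled, a useful device has a harder test to pass. The go/no-go result would then partly reflect referral flow, and the stated 10% type I error would be right only for a mix that happens to average 13%.

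**Working it through.** **Inputs.** From Section 14.0: null rates 0.10 (total and proximal gastrectomy) and 0.15 (esophagectomy); benchmark 0.13; target 0.05; stage 1 of 43 patients, continuing at 4 or fewer; 86 in total, success at 7 or fewer. I read the stage 1 stop as 5 or more leaks. Planned mix 57/29, from Sections 7.0 and 14.0.

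**Formula.** Let X1 and X2 be the leaks among the first and second 43 patients. For final cut-off r,

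P(success) = Σ (x = 0 to 4) P(X1 = x) · P(X2 ≤ r − x).

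Under a single rate p, X1 and X2 are Binomial(43, p). For a mix with g gastrectomies in a stage, the count is the sum of Binomial(g, 0.10) and Binomial(43 − g, 0.15), with its distribution obtained by convolution.

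**1. The plan's own figures.** With r = 7, P(success) is 0.0989 at p = 0.13 and 0.9012 at p = 0.05. The stated error rates and the 86 patients reproduce.

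**2. The benchmark at the planned mix.** (57 × 0.10 + 29 × 0.15)/86 = 10.05/86 = 11.7%, not 13%. A mean of 13% requires 0.10s + 0.15(1 − s) = 0.13, so s = 0.40, that is 40% gastrectomy.

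**3. No device effect, same mix in both stages.**

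| Gastrectomies per 43 | Share | Mean null rate | P(success), cut-off 7 | P(success), cut-off 6 |
|---|---|---|---|---|
| 0 | 0% | 15.0% | 0.037 | 0.018 |
| 14 | 33% | 13.4% | 0.083 | 0.045 |
| 17 | 40% | 13.0% | 0.097 | 0.054 |
| 22 | 51% | 12.4% | 0.126 | 0.072 |
| 29 | 67% | 11.6% | 0.177 | 0.108 |
| 34 | 79% | 11.0% | 0.222 | 0.140 |
| 43 | 100% | 10.0% | 0.321 | 0.219 |

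At exactly 57/29 (29 gastrectomies in stage 1, 28 in stage 2) the result is 0.173 with cut-off 7 and 0.105 with cut-off 6.

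**4. Separating the two causes.** Moving from 10% to about 17% at the planned mix is the benchmark mismatch. The spread around that value is the mix dependence. With cut-off 6, which roughly restores 10% at the planned mix, shares of 51% to 79% still give 0.072 to 0.140.

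**5. Timing against total.** With the total held at 57/29 but all 43 stage 1 patients having gastrectomy (then 14 in stage 2), P(success) is 0.186, against 0.173 for even accrual. The overall mix matters; its order hardly does.

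**6. The reverse error.** Suppose the device halves both rates, to 0.05 and 0.075. With cut-off 7, P(success) is 0.858 at 34 of 43 gastrectomies, 0.787 at 22 and 0.733 at 14.

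**7. Power cost of a lower cut-off.** At a uniform 5% leak rate, keeping 4 at stage 1, power is 0.901 with final cut-off 7, 0.844 with 6 and 0.735 with 5.

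**The case against.** The strongest reply is that a fixed pooled null with an expected mix, supported by intervals per procedure, is a common single-arm choice, and that success here only licenses further study. The plan names both services as recruitment sources with a definite split, and nothing in it points to a large departure. The pilot described in Section 3.3 ("We have performed a pilot study of 28 patients undergoing total gastrectomy via open or minimally-invasive approach") does not predict who will enrol in this trial. This stands, and it limits the size of the point to moderate departures from plan.

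It is also fair that much of the excess over 10% is the 13% versus 11.7% mismatch, which exists even if accrual goes exactly as planned. Step 4 therefore separates the two; the remaining mix dependence is smaller but does not vanish.

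Two stronger readings are tempting. A reader might infer that false success runs from 4% to 32% depending on which service enrols faster. Those are bounds, reached only if all 86 patients have one procedure; a faster service does not produce that, and the documents do not say that each clinic performs only one procedure. A reader might also infer that a gastrectomy-heavy first stage would by itself corrupt the result. Step 5 shows that it would not if the total mix holds.

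Finally, the target is an absolute 5%, so step 6 rests on an assumed halving of both rates and illustrates the reverse error, not the plan's stated power.

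**Conclusion.** The point holds in this limited form and should be addressed. The stated 10% type I error is met only when gastrectomies are about 40% of patients or fewer. With no device effect it is about 0.17 at the planned 57/29 and about 0.13 to 0.22 for gastrectomy shares of roughly 50% to 80%. With a final cut-off of 6, about 0.07 to 0.14 remains over the same shares. The procedure-specific confidence intervals would show the mix afterwards but would not alter the decision.

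Assumptions: null rates of exactly 10% and 15%, which the plan gives as approximate; the same mix in each stage, except where step 3 (57/29) and step 5 say otherwise; and the same rates at the participating site. The result is sensitive to the gastrectomy rate. At 8%, the low end of the institutional 8–15% range, false success with the present cut-offs would be about 0.29 at a two-to-one mix.

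**What to change.** In Section 14.0, state a null leak rate for each procedure group (total and proximal gastrectomy; esophagectomy). Take the final cut-off, and the stage 1 cut-off if needed, from the exact two-stage null distribution of the summed leaks at the procedure counts actually enrolled. Fix the look-up table before the stage 1 result is known. Restate type I error and power for the planned mix. This also resolves the 13% versus 11.7% mismatch.

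It needs no extra patients and no data beyond the operation performed, but it does cost power. Near the planned mix the final cut-off becomes about 6 (type I error about 0.105, slightly over the limit) or 5 (about 0.05) instead of 7. Power at a 5% leak rate then falls from 0.90 to about 0.84 or 0.74. The plan should say which it accepts, or reconsider the sample size if 90% power is to be kept.

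A cap on gastrectomies at the planned share is not a substitute. With the present cut-offs it leaves about 0.17 at the cap, and it does nothing about an excess of esophagectomies.
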